5.5.5 Permitted dose adjustments and interruptions of study treatment

Study drug dose adjustments are not permitted.

The patients with pulmonary exacerbations will continue in the study as scheduled once they have recovered and discontinued antibiotics administered for the exacerbation. If the patient continues in the study after the interruption of the study drug treatment, the schedule of visit/treatment cycle should be aligned with the original visit schedule.

Any interruption of the inhalation of study drug treatment must be recorded on the Dosage Administration Record CRF.

5.5.6 Rescue medication

Rescue medication for pulmonary exacerbations (including systemic antibiotics) and for bronchospasm is allowed. For concomitant treatments permitted see [Section 5.5.7](#). Use of rescue medication must be recorded on the Concomitant medications/Significant non-drug therapies CRF.

5.5.7 Concomitant medication

If a patient experiences a pulmonary exacerbation and/or worsening of the disease condition, he/she will be treated as deemed appropriate by the investigator. Following treatment for the pulmonary exacerbation and/or worsening of the disease condition, the patient will be expected to continue in the study as scheduled provided, in the opinion of the investigator, he/she can be safely returned to their pre-pulmonary exacerbation concomitant medications. In addition, if the patient requires any prohibited treatment listed in [Table 5-1](#), then he/she should be withdrawn from the study medication.

The following treatments **are permitted** between Visit 101 and the completion of the study/termination visit and should be accurately documented in the CRF:

- Antibiotics (parenteral or by mouth) are allowed for the treatment of pulmonary exacerbations as dictated by the patient's condition.
- Inhalation of study medication must be interrupted during i.v. aminoglycoside therapy. A window of 12 hours is recommended between stop of the study medication and initiation of i.v. aminoglycosides. Patients should restart inhalation of study medication within 24 hours after completing the i.v. treatment in order to complete the 112-day treatment epoch as close as possible to their initial study schedule, following completion of the course of i.v. aminoglycoside therapy.
- Inhalation of study medication may continue upon physician's decision, if the antibiotics used are other than aminoglycosides.
- Pre-planned systemic antibiotics in the absence of an AE (prophylaxis of pulmonary exacerbation) are permitted only during the follow-up epoch.

- Short term treatment (of a maximum of 28 consecutive days) with corticosteroids for the treatment of pulmonary exacerbations or other adverse events
- Macrolides (anti-inflammatory regimen):
 - Patients should have been initiated on oral chronic macrolide therapy (i.e. macrolides prescribed for more than 14 days) more than 28 days prior to study drug administration (Visit 101) and should remain on treatment through the completion/termination visit.
- Bronchodilators:
 - Patients should have been kept on the same regimen more than 28 days prior to the first study drug administration (Visit 101) through the completion/termination visit. If patients are on short-acting bronchodilators, they should be consistently used prior to each assessment and inhaled 15 to 90 minutes prior to any spirometric assessments. Long-acting bronchodilators should be inhaled at least 12 hours prior to any spirometric assessments.
 - To ensure a robust and valid assessment of FEV₁ at each visit, it is recommended that these are done consistently at a similar time of day (to account for diurnal effects) and following consistent use (or not) of prior bronchodilator therapy.
- Inhaled corticosteroids:
 - Patients should have been initiated on therapy more than 28 days prior to study drug administration (Visit 101) and should remain on an unaltered regimen through the completion/termination visit.
- Use of oxygen is allowed for acute events, such as exacerbation. Long-term oxygen therapy for chronic hypoxemia over >15 h per day is not allowed.

Selected information for all antibiotics and macrolides, corticosteroids and bronchodilators administered within 12 months prior to screening will be recorded in the CRF.

Caution for concomitant use

Based on the interaction profile for tobramycin following intravenous and aerosolized administration, concurrent and/or sequential use of TIP with other drugs with neurotoxic, nephrotoxic, or ototoxic potential should be avoided.

Other medicinal products that have been reported to increase the potential toxicity of parenterally administered aminoglycosides include:

- amphotericin B, ceftazidime, polymyxins (risk of increased nephrotoxicity);
- platinum compounds (risk of increased nephrotoxicity and ototoxicity);
- anticholinesterases, botulinum toxin (neuromuscular effects).

If the patient's condition/disease requires medications (including those listed above) which may potentially affect the systemic tobramycin levels (even the study drug is tobramycin inhalation powder), continuation of inhalation of study medication is at the investigator's discretion.

- If inhalation of study medication is continued during the following drug therapy, patients

will continue with the study schedule for the remainder of the study; however, therapeutic drug monitoring is strongly recommended.

- If inhalation of study medication is interrupted during the following drug therapy (either as a routine measure or due to elevated serum tobramycin levels), patients should restart inhalation of study medication in order to complete the 112-day treatment epoch as close as possible to their initial study schedule.

Caution should be exercised when prescribing TIP to patients with known or suspected neuromuscular disorders such as myasthenia gravis or Parkinson's disease. Aminoglycosides may aggravate muscle weakness because of a potential curare-like effect on neuromuscular function.

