5.6.3 Withdrawal of informed consent

- Section revised, as described above.

Section 9:

- Cohort is removed in the models for statistical analysis of primary and secondary variables due to confounding with treatment.
- Section 9.1. Information has been added to clarify that patients who are mistakenly randomized or who have not taken double blind study drug will be excluded from the full analysis set (FAS).
- Section 9.4.3 refers to a sensitivity analysis to account for patients who require treatment with anti-pseudomonal drugs for exacerbation: it was previously planned to exclude patient data from the start day of systemic anti-pseudomonal treatment for the relevant efficacy endpoints. This analysis will not be performed. Alternatively, for the primary endpoint only, multiple imputation will be implemented, as multiple imputation technique is more robust.

- Section 9.5.1.2 states that the proportion of patients with at least one pulmonary exacerbation, and the proportion of patients who permanently discontinue study drug due to pulmonary exacerbation will be analyzed using both logistic regression and time to event analysis. However, due to small sample size, these two endpoints will be evaluated using time to event analysis only. The annual rate of pulmonary exacerbations will be summarized only overall and not by exacerbations category due to small sample size.
- Section 9.5.1.3 refers to the use of anti-pseudomonal antibiotics. As anti-pseudomonal antibiotics used for treatment of pulmonary exacerbations are often used in combination, dose cannot be defined consistently. Therefore, the total amount (in doses) of anti-pseudomonal antibiotics used to treat pulmonary exacerbation during the treatment epoch and the study period will not be analyzed.

Summary of previous amendments

Amendment 2

Amendment rationale

The purpose of this protocol amendment is to revise the following enrolment criteria:

- Exclusion criterion 9a: The criterion was revised to reduce the number of disease-free survival years from 5 to 2 in patients with a history of cancer. Based on the tobramycin safety profile, there is no increased risk of cancer expected due to study medication.

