2.2 Secondary objectives

- To assess the effect of different doses of TIP administered o.d. and one b.i.d. dose and different regimens (TIP and TIP/placebo cyclical) on the frequency, rate (by patient-months), severity and time to onset of pulmonary exacerbations at the end of the treatment epoch and over the entire study, each compared to placebo.
- To assess the efficacy profile of different doses of TIP administered o.d. and one b.i.d. dose and different regimens (TIP and TIP/placebo cyclical), as measured by the time to first use, proportion of patients requiring anti-pseudomonal antibiotics (overall, oral, parenteral) and the duration of treatment of anti-pseudomonal antibiotics, each compared to placebo.
- To assess the time to first hospitalization, proportion of patients requiring hospitalization and the duration of hospitalization due to serious respiratory-related AEs (other than those regularly scheduled hospitalization that were planned prior to study start).
- To assess the pharmacokinetic concentrations of tobramycin in serum and in sputum from different doses of TIP administered o.d. and one b.i.d. dose and different regimens (TIP and TIP/placebo cyclical).
- To assess the antimicrobial efficacy of TIP over the entire study duration, as measured by the absolute change in *P. aeruginosa* colony forming units (CFU) in sputum from baseline to each post-baseline treatment visit and during the follow-up visits.
- To evaluate the safety profile of TIP in terms of clinical laboratory results.
- To evaluate the safety profile of TIP in terms of audiology findings throughout the treatment epoch (subgroup of all patients that are in enrolled at sites that are adequately equipped and trained to perform audiology assessments).
- To evaluate the safety profile of TIP in terms of acute change in forced expiratory volume at 1 second (FEV₁) % predicted values from pre-dose to 30±15 minutes after completion of study drug administration at the clinical site at visits during the treatment epoch.
- To evaluate the impact of treatment with TIP on the Respiratory Symptom Scale Quality of Life Questionnaire for Bronchiectasis (QOL-B) by measuring change from baseline to all post-baseline visits.

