6.4.3 Anti-pseudomonal antibiotic use

The proportion of patients having anti-pseudomonal antibiotic and duration of treatment (other than study drug) will be determined from the collection of concomitant medications during the study.

A list of anti-pseudomonal antibiotics can be found in [Appendix 12](#).

[figure not shown]

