To evaluate the effect of different doses of TIP on the change in P. aeruginosa bacterial load in sputum at Day 29	Change from baseline to Day 29 in P. aeruginosa density in sputum (log ₁₀ CFUs)	Section # 2.5.2
To assess the safety and tolerability with different doses of TIP and different regimens, on treatment epoch and over entire study duration	Safety: incidence rate of AEs/Serious AEs by MedDRA primary SOC and PT terms Tolerability: incidence and severity of local AEs (eg. cough, bronchospasm, dysgeusia, dry mouth, etc.)	2.7.1
Secondary		
To assess the antimicrobial efficacy of TIP over the entire study duration	Change from baseline to each post-baseline visit in P. aeruginosa density in sputum (log ₁₀ CFUs)	2.6.3.1
To assess the effect of different doses of TIP and different regimens on pulmonary exacerbation at the end of treatment epoch (Day 113) and over the study period	Time to first pulmonary exacerbation by exacerbation category Duration of pulmonary exacerbations by exacerbation category Exposure adjusted rate of exacerbations Proportion of patients with at least one pulmonary exacerbation by exacerbation category Proportion of patients who permanently discontinued study drug due to pulmonary	2.6.3.2

[figure not shown]
Objective	Endpoint	Statistical Analysis
To assess the efficacy profile of different doses of TIP and different regimens as measured by anti-pseudomonal antibiotics usage during the treatment epoch (through Day 113) and the study period	exacerbation Time to permanent study drug discontinuation due to pulmonary exacerbation Time to first use (overall, oral, and -parenteral) of anti-pseudomonal antibiotics usage	2.6.3.3
To assess the hospitalization (other than those regularly scheduled hospitalization that were planned prior to study start)	Proportion of patients used anti-pseudomonal antibiotics usage Duration of anti-pseudomonal antibiotics usage Time to first hospitalization due to serious respiratory-related AEs Number of hospitalizations due to serious respiratory-related AEs Proportion of patients requiring hospitalization due to serious respiratory-related AEs	2.6.3.4
To evaluate the safety profile of TIP in terms of clinical laboratory results	Duration of hospitalization due to serious respiratory-related AEs Laboratory results (hematology, serum chemistry, urine dipstick tests): means, mean changes from baseline, frequency/shift tables by visit	2.7.3

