2.6.3.3 Anti-pseudomonal antibiotics

Proportion of patients requiring anti-pseudomonal antibiotics

The proportion of patients requiring anti-pseudomonal antibiotics across the treatment epoch and across the entire study period will be summarized by treatment arm and by route of administration (overall, oral and parenteral).

Time to first use of anti-pseudomonal antibiotics across the entire study period

The time to first use of anti-pseudomonal antibiotics by route of administration (overall, oral and parenteral) will be analyzed using a Cox regression model stratified by baseline macrolide use. The model will include treatment as a fixed-effect factor, and number of pulmonary exacerbations in the 12 months prior to screening as a covariate. Six pairwise comparisons will be evaluated as specified in [Section 2.6.3](#). in addition two pairwise comparisons will be evaluated between pooled continuous regimens vs pooled placebo and, between pooled cyclic regimens and pooled placebo. The estimated adjusted hazard ratio for TIP over placebo will be displayed along with the associated 2-sided 95% CI.

The exposure adjusted rate of usage of anti-pseudomonal antibiotics across the entire study period

The number of anti-pseudomonal antibiotics across the entire study period will be analyzed by route of administration (overall, parenteral and oral) using a generalized linear model assuming the negative binomial distribution including treatment and baseline macrolide use as fixed-effect factors, and number of pulmonary exacerbations in the 12 months prior to screening as a covariate. The log time in study in years will be included as an offset variable in the model. Six pairwise comparisons will be evaluated as specified in [Section 2.6.3](#), in addition two pairwise comparisons will be evaluated between pooled continuous regimens vs pooled placebo and, between pooled cyclic regimens and pooled placebo. The adjusted rate of usage will be provided for each treatment arm. The estimated rate ratio together with the 2-sided 95% interval will be provided.

Duration of anti-pseudomonal antibiotic use across the entire study period

The duration of anti-pseudomonal antibiotic use (days) across the entire study period will be summarized by cohort, treatment arm and pooled cyclic and continuous regimens and by route of administration (overall, parenteral and oral).

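### The whole-study time-to-first-use and usage-rate analyses count planned follow-up prophylaxis as antibiotic use, and neither is run for the treatment epoch alone

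*Protocol*

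**What the plan says.** **What is permitted.** Protocol 5.5.7: "Pre-planned systemic antibiotics in the absence of an AE (prophylaxis of pulmonary exacerbation) are permitted only during the follow-up epoch". The follow-up epoch is 56 days, after a 112-day treatment epoch.

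**Where the data come from.** Protocol 6.4.3 takes antibiotic use from concomitant medication records. It names the proportion and the duration, "other than study drug) will be determined from the collection of concomitant medications during the study". Study drug is the only exclusion, and no other source is given for the remaining antibiotic measures.

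**What the objective is about.** Protocol 2.2 (repeated in SAP 1.2.2) lists time to first use, duration and the "proportion of patients requiring anti-pseudomonal antibiotics (overall, oral, parenteral"). The antibiotic objective in SAP Table 1-1 covers "anti-pseudomonal antibiotics usage during the treatment epoch (through Day 113) and the study period".

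**What is modelled.** SAP 2.6.3.3 has a Cox model headed "Time to first use of anti-pseudomonal antibiotics across the entire study period" and a negative binomial model with log time in study as offset: "The number of anti-pseudomonal antibiotics across the entire study period will be analyzed by route of administration". Only the descriptive proportion is also reported for the treatment epoch.

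**What else bears on it.** SAP 2.6.1.3 says the relevant antibiotics will be identified before database lock, without an indication rule. In Amendment 3, the rationale for the change to Protocol 9.5.1.3 notes that "anti-pseudomonal antibiotics used for treatment of pulmonary exacerbations are often used in combination", and total dose was dropped for that reason.

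**The concern.** A course scheduled in advance, with no adverse event behind it, says nothing about whether study treatment failed. If such courses enter the event definition, the hazard ratio and rate ratio mix therapeutic need with planned care, and the permitted planned care all falls in the last third of the study (56/168 days).

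The plan treats planned care as a non-event in neighbouring places. The hospitalization objective in Protocol 2.2 leaves out admissions scheduled before study start, and Protocol 7.2.1 leaves admission for preplanned prophylactic i.v. antibiotics out of the SAE definition. The antibiotic endpoints have no matching rule.

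The window that permitted prophylaxis cannot enter is the treatment epoch, and neither model is run there. Protocol 9.5.1 and SAP 2.6 both make the two windows the default, and Protocol 9.5.1.3 sets no other window. The SAP narrows both models to the whole study, and the visible text of its section on changes to protocol-specified analyses does not mention this.

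The second issue is the unit of the rate model. Two drugs given for one exacerbation, or an i.v.-to-oral switch in the overall count, could score one or two.

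**Working it through.** The documents give no event rate, effect size or power for any antibiotic endpoint, so there is no plan figure to reproduce. The sample size section concerns CFU only. All rates below are assumptions, used to show direction and range.

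**1. Does prophylaxis enter the event definition?** Permitted in follow-up (Protocol 5.5.7); recorded as concomitant medication, with only study drug excluded (6.4.3); follow-up included in the window (SAP 2.6.3.3); no indication rule (SAP 2.6.1.3). So yes, for any prophylactic drug classed as anti-pseudomonal.

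**2. Rate ratio, equal prophylaxis.** Let λ be therapeutic uses per patient-year on placebo, the true ratio be 0.60, T = 168/365.25 = 0.460 years, and p the share of each arm with one planned course:

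expected ratio = (0.60·λT + p) / (λT + p)

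| λ | p = 10% | p = 20% | p = 30% |
|---|---|---|---|
| 1 | (0.276+0.1)/(0.460+0.1) = 0.67 | 0.72 | 0.76 |
| 2 | (0.552+0.1)/(0.920+0.1) = 0.64 | 0.67 | 0.70 |

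**3. Hazard ratio for first use, equal prophylaxis.** Simulation with 20,000 patients per arm, constant therapeutic hazards with ratio 0.60, and prophylaxis starting uniformly between Day 113 and Day 169:

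| λ | p = 10% | p = 20% | p = 30% |
|---|---|---|---|
| 1 | 0.66 | 0.70 | 0.74 |
| 2 | 0.62 | 0.65 | 0.70 |

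With no prophylaxis the runs returned 0.588 and 0.600, so simulation error is about 0.01. Solving the expected Cox score equation numerically for the same set-up gives 0.665, 0.713, 0.750 (λ = 1) and 0.631, 0.658, 0.682 (λ = 2), which agrees within 0.02.

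**4. Unequal prophylaxis (λ = 2, rate ratio).**
- 30% placebo, 10% TIP: (0.552+0.1)/(0.920+0.3) = 0.53, away from 1.
- 10% placebo, 30% TIP: (0.552+0.3)/(0.920+0.1) = 0.84, toward 1.

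**5. Counting drugs instead of courses (rate model only).** Let q be the share of courses with two drugs, so E[m] = 1 + q and E[m²] = 1 + 3q. With Poisson courses the SE of the log rate is multiplied by √E[m²]/E[m]:
- q = 25%: √1.75/1.25 = 1.058
- q = 50%: √2.5/1.5 = 1.054
- q = 75%: √3.25/1.75 = 1.030

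With the same q in both arms the ratio stays at 0.60. With q = 50% placebo and 30% TIP it becomes 0.60 × 1.3/1.5 = 0.52; with the shares reversed, 0.60 × 1.5/1.3 = 0.69.

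**6. Available precision.** With 107 randomized at 2:2:1, a pooled regimen has 107 × 2/5 ≈ 43 patients and pooled placebo 107/5 ≈ 21. Assuming 40% use on placebo and HR 0.60, expected events are 21.4 × 0.40 = 8.6 and 42.8 × (1 − 0.6^0.6) = 11.3. SE(log HR) = √(1/8.6 + 1/11.3) ≈ 0.45, and the 95% interval is about 0.25 to 1.46.

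**The case against.** Several points on the other side stand.

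- **A clean measure exists.** The treatment-epoch proportion, overall and by route, is free of permitted prophylaxis. Grammatically, the objective attaches the word requiring to that proportion; the other measures speak of use. Analysing all use is defensible as a supportive view. It does not explain why both models leave out the window that Table 1-1 and the two default statements include.
- **The scope is limited.** Only anti-pseudomonal prophylaxis matters. Macrolides are not in Protocol Table 24-1, although that list is not exhaustive. The identification step before lock could still add an indication rule, but as written it settles only which drugs count.
- **The effect is small against the noise.** A shift from 0.60 to about 0.7 lies well inside an interval of 0.25 to 1.46, and the SAP introduction calls all inference exploratory after early closure. That lowers the priority, but the event definition still differs from the objective.

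A reader might go further and infer that the plan counts each drug of a combination and so dilutes the effect. The documents do not support this. SAP 2.6.3.3 never defines the unit. Drug-level counting would touch only the rate model and, with equal combination use, leaves the ratio unchanged. The 3-6% is also for Poisson courses; overdispersion makes the relative increase smaller.

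A reader might also infer that Table 1-1 promises the usage rate through Day 113. It does not list that rate. The case for running the rate model there rests on the objective in that row and on the default in Protocol 9.5.1 and SAP 2.6.

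**Conclusion.** The point holds in a limited form. As written, planned follow-up prophylaxis with an anti-pseudomonal drug is an event in the whole-study time-to-first-use and usage-rate analyses, and neither is run for the treatment epoch, where such prophylaxis is not permitted.

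A true ratio of 0.60 would appear as about 0.62-0.74 (hazard ratio) or 0.64-0.76 (rate ratio). This assumes one planned course in 10-30% of patients, equal across arms, 1 to 2 therapeutic uses per patient-year on placebo, and the same treatment ratio throughout the 168 days. None of these rates is in the documents, and the actual frequency of prophylaxis could be near zero. It would be wrong to read the plan as certainly biased toward no effect: that direction needs similar prophylaxis across arms, and unequal use can move the ratio either way.

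The undefined counting unit is a lesser, separate matter of missing detail. Its cost is a few percent of standard error, plus a bias of unknown sign if combination use differs by arm. Overall this is worth correcting before lock, at modest priority, because the analyses are secondary and exploratory.

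**What to change.** 1. In the antibiotic review already planned before database lock, flag planned prophylaxis under blind. Do not count flagged courses as events in time to first use or the rate, and state that the patient stays at risk afterwards. An all-use analysis can be kept as supportive.
2. Run the Cox and negative binomial models through Day 113 as well, with the offset matched to that window.
3. In the rate model, count courses: overlapping or contiguous records form one course, with a stated gap rule, and a rule for courses that mix oral and parenteral drugs in the by-route analyses.

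The cost is some SAP wording, a little programming and a blinded judgement on indication. If the medication page does not record the reason for use, the flag has to come from matching dates to the exacerbation and adverse event records, and unclear cases need a default. No new data collection and no change to clinical management is involved.

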The last administration of study medication will be in the morning at Visit 106 (Day 113). Administration of any short-acting bronchodilator should occur 15 to 90 minutes prior to the spirometric assessments. Any other inhaled medications should have been taken prior to administration of study drug and any chest physiotherapeutic measures shall have been completed previously. If applicable, any long-acting bronchodilator prescribed to the patient should have been taken within the last 12 hours prior to the spirometric assessments; otherwise a short-acting bronchodilator shall be taken as described above. Also, the examinations which should be performed before study drug inhalation defined in [Table 6-1](#) need to be completed prior to study drug administration. To ensure a robust and valid assessment of FEV₁ at each assessment it is important that these are done consistently at a similar time of day (to account for diurnal effects) and following consistent use (or not) of prior bronchodilator therapy.

All dosages prescribed and dispensed to the patient must be recorded on the Dosage Administration Record CRF.

All kits of investigational treatment assigned by the IRT will be recorded/databased in the IRT.

The investigator must promote compliance by instructing the patient to take the study treatment exactly as prescribed and by stating that compliance is necessary for the patient's safety and the validity of the study. The patient must also be instructed to contact the investigator if he/she is unable for any reason to take the study treatment as prescribed.

If any faults or complaints are identified with the device, these should be returned to Novartis with a completed Device Return Form. The forms will be supplied to each investigator site by the Field Monitor.

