6.4.4 Pulmonary exacerbations

The rate, duration and primary precipitating factors of pulmonary exacerbations will be assessed during the study. Pulmonary exacerbation episodes will be collected on a specific CRF.

Pulmonary exacerbations are defined as: events for which it is clinically determined by the site investigator that antibiotic therapy is required AND at least 3 of the following 6 symptoms, signs, or findings were present outside of normal variation:

1. Increased sputum volume, or change in viscosity / consistency or purulence for more than 24 hours;
2. Increased shortness of breath at rest or on exercise for more than 24 hours;
3. Increased cough for more than 24 hours;
4. Fever of $\geq 38^{\circ}$ Celsius within the last 24 hours;
5. Increased malaise / fatigue / lethargy for more than 24 hours;
6. A reduction in forced expiratory volume in the first second of expiration (FEV₁) or forced vital capacity (FVC) of least 10% from screening;

A worsening of symptoms that either does not meet the above symptom definition but is treated by the investigator with antibiotics, or that meets the symptom definition but is not treated with antibiotics, is not considered a pulmonary exacerbation for the study.

For the above reported signs and symptoms, additional information will be collected to document if the reported signs and symptoms last for more than 48 hours.

Patients should be advised to contact the site when experiencing a pulmonary exacerbation for advice. An unscheduled visit should occur within 2 working days of the event to confirm the diagnosis, unless the patient is hospitalized and thus unable to attend the site. AEs/SAEs, concomitant medications, and safety laboratory exams should be captured, as appropriate.

The start date for a pulmonary exacerbation recorded in the CRF should be the first day of symptom worsening of at least 3 of the 6 symptoms, as defined above. The end of a pulmonary exacerbation episode is marked by the return to pre-exacerbation symptom status.

An exacerbation might result in missed or rescheduled visit(s) and missing associated CRF data in some circumstances.

Patients who develop a pulmonary exacerbation between screening and prior to treatment will be screen failed but will be permitted to be re-screened once the inclusion/exclusion criteria have been met (see exclusion criteria).

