6.4.5 Pulmonary function tests

Pulmonary function testing will be performed locally at the site using locally available spirometry equipment. FEV₁, [REDACTED] values will be recorded on the CRF as absolute volume measurements. The pre-dose values will be used as efficacy measurements.

Please refer to the Spirometry Guidance, in [Appendix 5](#) for full details on scheduling and performing spirometry.

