6.5.6 Bronchial hyperreactivity

Bronchial hyperreactivity will be measured as the acute relative change from pre-dose to 30 ± 15 minutes post-dose in FEV₁% predicted at Visits 101, 102, 103, 104, 105 and 106. A change of 20% or more is considered a clinically significant indication of bronchospasm/bronchial hyperreactivity.

It is at the investigators discretion to initiate treatment with a bronchodilator prior to inhalation of study treatment or to consider discontinuation of study treatment in the case that bronchial hyperreactivity is experienced.

If a patient prematurely discontinues study drug, airway reactivity should be assessed at the treatment discontinuation (TD) visit provided the patient agrees to inhale study medication during the visit.

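### Protocol 5.5.4 and 5.5.7 give opposite timing for long-acting bronchodilators before spirometry: one rule is needed, and the hearing stop in 6.5.7 should be aligned with 5.6.2

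*Protocol*

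**What the plan says.** **Spirometry preparation.** Protocol 5.5.4 says that "any long-acting bronchodilator prescribed to the patient should have been taken within the last 12 hours prior to the spirometric assessments". For a patient who has not done so, the section gives a fallback: "otherwise a short-acting bronchodilator shall be taken as described above", meaning 15 to 90 minutes before the test. The same section adds: "Any other inhaled medications should have been taken prior to administration of study drug". Protocol 5.5.7 says: "Long-acting bronchodilators should be inhaled at least 12 hours prior to any spirometric assessments". Both sections, and Appendix 5, ask for consistent conditions from visit to visit.

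**Where spirometry is used.** Protocol 6.4.5: "The pre-dose values will be used as efficacy measurements". In 6.4.4, sign 6 of the exacerbation definition begins "A reduction in forced expiratory volume in the first second of expiration" and requires a fall of 10% in FEV1 or FVC from screening. For a suspected exacerbation, "An unscheduled visit should occur within 2 working days of the event to confirm the diagnosis". In 6.5.6, a 20% change in FEV1 % predicted from before to 30±15 minutes after dosing, at Visits 101 to 106, indicates bronchial hyperreactivity.

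**Hearing.** Protocol 5.6.2 stops treatment for a loss of 20 dB or more if the cause is sensorineural, and monitors until recovery or study closure. Protocol 6.5.7 stops treatment for a 20 dB drop with no condition on cause, and monitors until recovery or the follow-up visit. It orders bone conduction testing but does not say how the result is used.

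**eGFR.** Protocol 5.6.2 lists eGFR of 50 or less among the circumstances in which treatment must stop. Table 14-1 repeats that threshold in the row for a creatinine rise of 25 to <50%, with a recheck in 2 to 5 days and then a decision left to clinical judgement.

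**The concern.** One section asks for spirometry under the effect of the long-acting drug. The other asks for it at 12 hours or later. Two sites can each follow the protocol in good faith and test similar patients under different conditions, and one site can change its practice between visits depending on the section it consults.

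The measurements at stake are an efficacy measure, an exacerbation sign and a safety measure that is a named secondary objective in a trial designed to compare tolerability. Protocol 6.5.6 itself treats bronchodilation as relevant to the post-dose test: when hyperreactivity is experienced, "It is at the investigators discretion to initiate treatment with a bronchodilator prior to inhalation of study treatment".

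On hearing, a patient with a conductive loss of 20 dB could be stopped at one site and kept on drug at another.

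**Working it through.** No plan figure needs reproducing. The check is a comparison of the texts.

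**1. Long-acting bronchodilator.** Let t be the hours between the long-acting dose and spirometry.

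| Situation | 5.5.4 | 5.5.7 |
|---|---|---|
| t < 12 | met | not met |
| t = 12 | met | met |
| t > 12, short-acting dose 15–90 min before | met through the fallback | met |
| t > 12, no short-acting dose | not met | met |

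Apart from the single point t = 12, only the third row satisfies both. It is what 5.5.4 offers when its main instruction has not been followed. Complying with both sections therefore means making the exception the standard preparation, which neither section says.

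**2. Does the consistency wording settle it?** No. It limits drift within a patient but does not choose a rule, so preparation can still differ between sites.

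**3. Unscheduled visits.** If spirometry is done at an exacerbation visit, 5.5.4 can always be met through its fallback. A patient who has just taken the long-acting drug would have to wait up to 12 hours under 5.5.7.

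**4. What the discrepancy reaches.**
- Pre-dose FEV1: the level depends on preparation.
- Sign 6: it refers back to screening, so it is affected if preparation differs between screening and the later test. It is one of at least three signs needed, and the investigator must also decide that antibiotics are required. It is decisive only when exactly two other signs are present.
- Hyperreactivity: a same-visit change, so the starting level largely cancels. What remains is that recent bronchodilation can blunt the response.
- Day 29 log10 CFU: not affected.

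**5. Bias or noise?** Treatment is blinded within cohort, so there is no evident reason for preparation to differ between arms of a cohort. The expected effect is mainly extra variability.

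**6. Hearing.** For a loss of 20 dB or more:
- Sensorineural: stopped under both sections.
- Not sensorineural: stopped under 6.5.7, not required by 5.6.2.

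The disagreement is confined to the second case, and 6.5.7 errs on the cautious side. The different monitoring ends matter little, because 6.5.7 already repeats abnormal audiology through the end-of-study visit.

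**7. eGFR.** The stop in 5.6.2 is mandatory, and that section describes the Appendix 2 abnormalities left to clinical judgement as additional ones. A site that stops treatment and then rechecks as Table 14-1 asks has followed both.

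**The case against.** The strongest defence is that the third row of the table is a workable common rule: withhold the long-acting drug for 12 hours, then give a short-acting dose. That is feasible, and it rules out the inference that no patient can comply. A reader might argue that the route fails for a morning long-acting dose because 5.5.4 wants other inhaled medication taken before study drug. That is a strained reading: a dose the previous morning or evening also precedes study drug. What stands is that a site has to work this route out, and nothing tells it to.

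A reader might also try to put a size on the effect. If a long-acting drug raised FEV1 by an assumed 2%, 5% or 10%, moving from on drug at screening to off drug later would show a fall of 1 − 1/(1+d) = 2.0%, 4.8% or 9.1% with no change in disease. The documents do not support using this as a magnitude. They give no drug effect. They ask for consistent use within a patient. Under 5.5.4, a patient without a recent long-acting dose takes a short-acting one and so is not off bronchodilator. Similarly, with 107 randomized and exact ratios assumed, a cohort's placebo arm holds 107/3/5 = 7.1 patients, so one patient moves its rate by about 14 percentage points. That is true of any patient and any event, and says nothing about frequency.

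A third tempting reading is that Table 14-1 overrides or contradicts the mandatory eGFR stop. It does not, for the reason in step 7.

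On hearing, 6.5.7 can be read as a sequence in which bone conduction establishes the cause that 5.6.2 requires. That is a sensible reading, but 6.5.7 does not state it and its own withdrawal sentence is unconditional.

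**Conclusion.** The bronchodilator conflict is real, sits in the current protocol text and is unresolved. It should be corrected. Its expected consequence is added noise in pre-dose FEV1, in exacerbation sign 6 and in bronchial hyperreactivity, which the SAP reports descriptively. How much noise cannot be derived, because the documents give neither the number of patients on long-acting drugs nor the size of the drug effect. The view that this is noise rather than bias rests on within-cohort blinding.

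The hearing rules differ only for non-sensorineural loss and in the end of monitoring. This is a secondary point. The eGFR wording is an overlap, not a contradiction. The primary CFU comparison, its sample size and its error control are untouched.

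**What to change.** 1. **Bronchodilator.** Replace the 5.5.7 sentence with the 5.5.4 rule: long-acting dose no more than 12 hours before spirometry, otherwise a short-acting dose 15 to 90 minutes before. Apply it the same way at every visit for a given patient, including unscheduled exacerbation visits. This rule covers every case and can be met without delay at an unscheduled visit. Acknowledge its small downside, that recent bronchodilation may blunt post-dose bronchospasm and make the hyperreactivity test somewhat less sensitive.
2. **Hearing.** State in 6.5.7 that the bone conduction result decides whether a 20 dB loss is sensorineural and so requires discontinuation under 5.6.2. Use one monitoring end in both sections.
3. **eGFR.** At most, add a cross-reference to 5.6.2 in the creatinine 25 to <50% row of Table 14-1.

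The cost is one clarifying amendment and a memo to sites, with no added visit or assessment. Recruitment has stopped, so the change reaches only patients still on study. An extra analysis split by baseline bronchodilator use is not needed: SAP 2.3 lists bronchodilators without class or dose time, so the split would not capture the timing at issue.
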